5.4 DURATION OF THERAPY

In the absence of treatment delays due to adverse event(s), treatment may continue without a limitation on the number of cycles, unless one of the following criteria applies:

- ❖ Disease progression after two cycles or later of therapy
- ❖ Intercurrent illness that prevents further administration of treatment
- ❖ Unacceptable adverse event(s)
- ❖ Patient decides to withdraw from the study
- ❖ General or specific changes in the patient's condition render the patient unacceptable for further treatment in the judgment of the investigator
- ❖ Patient becomes pregnant
- ❖ Patient loses the ability to freely provide consent through imprisonment or involuntary incarceration for treatment of a psychiatric or physical illness
- ❖ Patient achieves complete remission (CR), and the patient and investigator feel that discontinuation of cabozantinib is in the patient's best interests, or
- ❖ Patient achieves a level of response that qualifies him or her for another therapy for which they provide consent, such as high dose therapy with autologous stem cell transplantation.

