5.7. DOSING DELAYS / DOSE MODIFICATIONS

In Phase I of this study we will determine the MTD among three doses. DLTs will be based solely on adverse events that occur during cycle 1. The definition of DLT includes:

- a. Any non-hematological toxicity Grade ≥ 3 , except for alopecia and nausea uncontrolled by medical management.
- b. Grade 4 neutropenia lasting more than 5 days.
- c. Febrile neutropenia of any duration (ANC $<1.0 \times 10^9/L$ fever $\geq 38.5^{\circ}\text{C}$)
- d. Grade 4 thrombocytopenia, or Grade 3 thrombocytopenia with bleeding, or any requirement for platelet transfusion
- e. Grade 4 anemia, unexplained by underlying disease.

We will study three dose levels using the 3+3 algorithm, so that we will accrue a minimum of 3 patients and a maximum of 18 patients in Phase I. The initial dose of cabozantinib for all patients treated on this study will be 20 mg P.O. daily, which is designated dose level -1. In the event that dose modifications are needed for toxicities, the following additional dose levels will be used:

Dose Level	Cabozantinib Dose
-1	20 mg p.o., daily
0	40 mg p.o., daily
+1	60 mg p.o., daily

To allow for optimal experimental design, capped dose of carfilzomib of 27 mg/m^2 will be used in the study without dose escalations or de-escalations. Given the potential for compounding/worsening toxicities with the addition of cabozantinib to carfilzomib, patients eligible for the trial will have to have had very good tolerance to carfilzomib in the context of treatment regimens they were receiving, with resolved prior carfilzomib toxicities to grade 1 or better, and no toxicities due to carfilzomib that required dose reductions to less than 27 mg/m^2 as dose adjustments will be allowed in the cabozantinib only. Stopping of carfilzomib however will be allowed if the adverse events secondary to carfilzomib that require its stopping are observed/met.

Specific dose modifications guidelines will be followed for the adverse events nausea, vomiting, diarrhea, neutropenia, and thrombocytopenia, and are detailed below. If a patient experiences several adverse events and there are conflicting recommendations, the investigator should use the recommended dose adjustment that reduces the dose to the lowest level.

Event Name	Diarrhea
Grade of Event	Management/Next Dose for Cabozantinib
\leq Grade 1	No change in dose
Grade 2	Hold until \leq Grade 1. Resume at same dose level.

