Grade 3	Hematologic (neutropenia, thrombocytopenia, anemia)	
Withhold carfilzomib dose.
 
If fully recovered before next scheduled dose, continue at same dose level.
 
If recovered to Grade 2 neutropenia or Grade 3 thrombocytopenia, reduce dose by one dose level: from 27 mg/m² to 20 mg/m², OR from 20 mg/m² to 15 mg/m².
 
If tolerated, the reduced dose may be escalated to the previous dose at the discretion of the physician.
 
TMA: If TMA is suspected, hold carfilzomib and manage per standard of care. If TMA is confirmed and related to carfilzomib, permanently discontinue carfilzomib. If TMA is excluded, may restart carfilzomib.
	
Withhold cabozantinib.
 
If the relevant lab value recovers to: $1.0 \times 10^9/L$ for ANC, 8 g/dL for hemoglobin, or $50 \times 10^9/L$ for platelets, resume cabozantinib treatment at same dose level. If the relevant lab value takes more than 3 weeks to recover to the level described above, restart cabozantinib administration at the next lower dose. If a second hold is required for the same event, administer cabozantinib at the next lower dose for subsequent cycles (for those subjects starting at 40 mg dose, cabozantinib would be discontinued if second hold required).

	Hepatic Toxicity	
25% dose reduction in case of baseline or treatment emergent mild or moderate hepatic impairment. Withhold carfilzomib until resolved or returned to baseline. After resolution, consider if restarting is appropriate. May be restarted at the dose (from 27 mg/m² to 20 mg/m², OR from 20 mg/m² to 15 mg/m²) with frequent monitoring of liver function. If tolerated, the reduced dose may be escalated to the previous dose at the discretion of the physician. Monitor liver enzymes regularly, regardless of baseline values, and modify dose based on toxicity.
	

Event Grade (NCI CTC V4.03) and Category		Action by Agent	
Grade	Adverse Event	Carfilzomib	Cabozantinib
	Renal	Serum creatinine ≥ 2 times baseline, CrCl < 15 mL/minute or CrCl decreases to $\leq 50\%$ of baseline, or patient requires dialysis: Withhold dose and monitor renal function. If renal toxicity is due to carfilzomib, resume dosing when renal function has improved to within 25% of baseline; resume with a reduced dose by 1 dose level.	

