	Cardiac Toxicity: Grade 3 or 4, new onset or worsening of: 1. Congestive heart failure; 2. Decreased left ventricular function 3. Myocardial ischemia	Withhold until resolved or returned to baseline. After resolution, consider if restarting carfilzomib at a reduced dose is appropriate (from 27 mg/m ² to 20 mg/m ² , OR from 20 mg/m ² to 15 mg/m ²). If tolerated, the reduced dose may be escalated to the previous dose at the discretion of the physician.	
	Peripheral Neuropathy	Withhold until resolved or returned to baseline. After resolution, consider if restarting carfilzomib at a reduced dose is appropriate (from 27 mg/m ² to 20 mg/m ² , OR from 20 mg/m ² to 15 mg/m ²). If tolerated, the reduced dose may be escalated to the previous dose at the discretion of the physician.	
	Clinically significant Non-hematologic	Withhold until resolved or returned to baseline. After resolution, consider if restarting carfilzomib at a reduced dose is appropriate (from 27 mg/m ² to 20 mg/m ² , OR from 20 mg/m ² to 15 mg/m ²). If tolerated, the reduced dose may be escalated to the previous dose at the discretion of the physician.	Withhold cabozantinib until recovery to Grade 1 or screening value. Administer cabozantinib at the next lower dose for subsequent cycles, unless further dose reduction is required. If a second hold is required for the same event, administer cabozantinib at lower dose for subsequent cycles. For those subjects starting at 40 mg dose, cabozantinib would be

Event Grade (NCI CTC V4.03) and Category		Action by Agent	
Grade	Adverse Event	Carfilzomib	Cabozantinib
		PRES: If PRES is suspected, hold carfilzomib. Consider evaluating with MRI for onset of symptoms suggestive of PRES. If PRES if confirmed, permanently discontinue carfilzomib. If PRES is excluded, may resume carfilzomib at same dose if clinically appropriate.	discontinued if second hold required.

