10.4 Stopping Rules

A response rate of 5% or less will be considered as clinically insignificant, while a response rate of 25% will be considered as clinically significant. With alpha= 0.05 and power of 0.80, the Simon optimal 2-stage design requires minimum enrollment of 9 patients in the first stage. The hypothesis will be rejected and enrollment will cease if no response is seen in the 9 patients. If at least 1 response is seen in the first 9 patients, another 14 patients will be accrued, for a total of 17 evaluable patients. At the end of the trial, the drug will be rejected if no more than 2 responses are seen in the total of 17 evaluable patients.

Cabozantinib will be taken in 20-mg capsules to reach the target dose levels as determined during the phase I and phase II portions of the study. This therapy will be continued without a cap on the number of allowed cycles, unless one of the following occurs:

- ❖ Disease progression after two cycles or later of therapy
- ❖ Intercurrent illness that prevents further administration of treatment
- ❖ Unacceptable adverse event(s)
- ❖ Patient decides to withdraw from the study
- ❖ General or specific changes in the patient's condition render the patient unacceptable for further treatment in the judgment of the investigator
- ❖ Patient becomes pregnant
- ❖ Patient loses the ability to freely provide consent through imprisonment or involuntary incarceration for treatment of a psychiatric or physical illness
- ❖ Patient achieves complete remission (CR), and the patient and investigator feel that discontinuation of cabozantinib is in the patient's best interests, or

- ❖ Patient achieves a level of response that qualifies him or her for another therapy, such as high dose therapy with autologous stem cell transplantation.

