
14. Patients who have undergone any recent major surgery must have done so at least 4 weeks prior to starting therapy with cabozantinib, with the following exceptions:
 
 ❖ Vertebroplasty and/or kyphoplasty, which must have been performed at least 1 week prior to starting cabozantinib ❖ Planned elective surgery unrelated to the patient's diagnosis of multiple myeloma, such as hernia repair, may be allowed, at the discretion of the principle investigator, as long as it was performed at least 2 weeks prior to starting cabozantinib, and patients have recovered fully from this procedure 	[] [] 14.

15. HIV seropositive patients with acceptable organ function who meet the patient selection criteria, and who are not on combination antiretroviral therapy, and whose absolute CD4⁺ count is ≥ 400 cells per cubic millimeter of blood, will be eligible. However, HIV positive patients on combination antiretroviral therapy will be ineligible, because of the potential for pharmacokinetic interactions with cabozantinib.
	[] [] 15.

16. Screen subjects prior to treatment whose baseline hepatitis B serologic status is unknown. Subjects, who are chronic carriers of hepatitis B virus, please screen with hepatitis B DNA to exclude active viral replication and monitor hepatitis B DNA at regular intervals while on study.
	[] [] 16.

17. Sexually active subjects (men and women) must agree to use medically accepted barrier methods of contraception (eg, male or female condom) during the course of the study and for 4 months after the last dose of study drug(s), even if oral contraceptives are also used. All subjects of reproductive potential must agree to use both a barrier method and a second method of birth control during the course of the study and for 4 months after the last dose of study drug(s). Male subjects must agree to not donate sperm for at least 90 days after the last dose of Carfilzomib.
	[] [] 17.

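### The sperm-donation bar runs from the last carfilzomib dose only, so it can lapse while a man is still taking cabozantinib (low priority)

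*Combined protocol and SAP*

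**What the plan says.** Item 17 has the same text in Section 3.1 and in Appendix A. Its contraception sentences cover the course of the study and continue "for 4 months after the last dose of study drug(s), even if oral contraceptives are also used". Its last sentence, on donation, names one drug and does not mention the study period: "Male subjects must agree to not donate sperm for at least 90 days after the last dose of Carfilzomib". Nothing else in the documents supplied mentions sperm donation.

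The two drugs are managed separately:

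- Section 5.7: "Stopping of carfilzomib however will be allowed if the adverse events secondary to carfilzomib that require its stopping are observed/met".
- Table 5-1 (Section 5.7.1), thrombotic microangiopathy (TMA): "If TMA is confirmed and related to carfilzomib, permanently discontinue carfilzomib". The cabozantinib cell of that row holds the drug and resumes it when counts recover.
- Table 5-1, progressive multifocal leukoencephalopathy (PML): carfilzomib ends on a confirmed diagnosis, and no cabozantinib action is given.
- Table 5-1, clinically significant grade 3 non-hematologic events: for carfilzomib, "After resolution, consider if restarting carfilzomib at a reduced dose is appropriate"; for cabozantinib, "Administer cabozantinib at the next lower dose for subsequent cycles, unless further dose reduction is required".

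Duration is open-ended. Section 5.4 says "treatment may continue without a limitation on the number of cycles, unless one of the following criteria applies", and Section 10.4 says of cabozantinib "This therapy will be continued without a cap on the number of allowed cycles". Neither list of reasons for ending therapy includes stopping carfilzomib.

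**The concern.** The donation sentence is adequate for carfilzomib. The problem is what it leaves out for cabozantinib. If carfilzomib is stopped and cabozantinib continues, the 90 days start on the carfilzomib stop date and can run out during daily cabozantinib dosing. A site that applies the checklist exactly would then have no bar to enforce.

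What is at stake is narrow. The contraception sentences already cover ordinary conception during cabozantinib treatment and for 4 months afterwards. Voluntary donation is the one route left open. Item 17 asks men to take precautions for both drugs, yet the clock for this one precaution follows only one of them.

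**Working it through.** There is no figure in the plan to reproduce, so this is a check of the text followed by a day count.

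**Which carfilzomib stops open the gap.** TMA, PML and a grade 3 non-hematologic event after which carfilzomib is not restarted can all leave cabozantinib running. Hypertensive crisis and malignant hypertension do not count, because Table 5-1 ends both drugs for them. Posterior reversible encephalopathy syndrome is also left out: it ends carfilzomib, and the table ends cabozantinib for reversible posterior leukoencephalopathy syndrome.

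**Inputs.** Cycles last 28 days and cabozantinib is taken daily on days 1–28 (Section 5.1.1). Carfilzomib is given on days 1, 2, 8, 9, 15 and 16 (Section 8.2.4). The bar is 90 days (item 17). The cabozantinib half-life is about 55 hours (Section 2.2.2).

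**Formula.** Let the last carfilzomib dose fall on day d of cycle c. The bar ends on study day 28(c − 1) + d + 90. Assume the last cabozantinib dose is on day 28 of cycle c + m, which is study day 28(c + m). Days of cabozantinib dosing after the bar has ended are

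28(c + m) − [28(c − 1) + d + 90] = 28m − 62 − d.

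| Further cycles m | d = 16 | d = 1 | Dosing after the bar ends |
|---|---|---|---|
| 0 | −78 | −63 | none |
| 1 | −50 | −35 | none |
| 2 | −22 | −7 | none |
| 3 | 6 | 21 | 6 to 21 days |
| 5 | 62 | 77 | 62 to 77 days |

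**Example.** With c = 1 and d = 16, the bar ends on day 16 + 90 = 106. Cabozantinib through cycle 6 ends on day 6 × 28 = 168. That leaves 168 − 106 = 62 days of dosing with no bar.

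**Both drugs stopped in the same cycle (m = 0).** The bar ends 63 to 78 days after the last cabozantinib dose. That is 63 × 24 / 55 = 27.5 to 78 × 24 / 55 = 34.0 half-lives, so this case leaves no gap.

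**How many men.** Section 2.1 quotes 11,170 men among 20,180 new cases, a share of 0.5535. Applied to the accrual target of 32, this is 0.5535 × 32 = 17.7 men. The documents give no rate for stopping carfilzomib and then staying on cabozantinib for more than 90 days. An assumed 2% gives 17.7 × 0.02 = 0.4 men, and 10% gives 17.7 × 0.10 = 1.8 men.

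**The case against.** The strongest reply is that no harm is shown. The reproductive toxicology in Section 2.2.3 is embryo-fetal, from dosed pregnant rats, and the rest is deferred to the investigator's brochure. A sentence naming carfilzomib may have been meant as a carfilzomib rule only. This stands as a limit on importance: the documents do not settle whether cabozantinib needs its own bar on toxicological grounds. It does not remove the inconsistency, since item 17 already requires men to use contraception through cabozantinib and for 4 months after it.

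The second reply is that long cabozantinib monotherapy is inferred and never described. The trial tests the combination. An investigator could end all treatment for an unacceptable adverse event, and confirmed progression removes the patient. That makes the situation uncommon, but it remains permitted, and the agent-by-agent table leads to it without any deviation.

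Two of the routes need qualifying. The grade 3 non-hematologic route needs a lower cabozantinib dose to go to, and there is none below 20 mg, so as written it works only for men on 40 or 60 mg. The TMA row is not silent on cabozantinib: it has general hold-and-resume text tied to blood counts, with discontinuation at a second hold for those who started at 40 mg. The resume instruction supports the gap.

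Finally, the head count is of men who reach the window, and men who would actually donate are fewer. Section 2.1 gives an average age at diagnosis of 65–70. The 90 days is a minimum. The consent pages were not available, so a wider bar there cannot be excluded. All of this supports a low priority, but an eligibility criterion that sites sign should be complete without relying on consent text.

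**Conclusion.** The concern holds as a low-priority wording gap. The lapse requires that carfilzomib stops first and that cabozantinib then continues for more than 90 days. The day counts assume that cabozantinib runs to the end of its last cycle. The head count also rests on the assumed 2% to 10% and on a national sex split carried over to this trial. The gap in the rule depends on neither of those two figures. No estimate of reproductive risk is made, and the trial's endpoints, analyses and sample size are untouched.

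**What to change.** In Section 3.1 item 17 and Appendix A item 17, reword the donation sentence along these lines: *Men must not donate sperm while on study or for at least 90 days after their final dose of cabozantinib or carfilzomib, whichever is later.* Replacing 90 days with the 4 months used elsewhere in the item would make it uniform, but this is optional. Any consent text that repeats the sentence should be changed to match.

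The cost is one sentence in two places, plus the consent form if it applies. No visit, procedure or patient is added, and the change can go in with the next amendment made for other reasons.

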Appendix B: MDASI - MM TOOL

M. D. Anderson Symptom Inventory (MDASI - MM)

Part I. How **severe** are your symptoms?

People with cancer frequently have symptoms that are caused by their disease or by their treatment. We ask you to rate how severe the following symptoms have been ***in the last 24 hours***. Please fill in the circle below from 0 (symptom has not been present) to 10 (the symptom was as bad as you can imagine it could be) for each item.

	Not Present										As Bad As You Can Imagine	
	0	1	2	3	4	5	6	7	8	9	10	
1. Your pain at its WORST?												
2. Your fatigue (tiredness) at its WORST?												
3. Your nausea at its WORST?												
4. Your disturbed sleep at its WORST?												
5. Your feelings of being distressed (upset) at its WORST?												
6. Your shortness of breath at its WORST?												
7. Your problem with remembering things at its WORST?												
8. Your problem with lack of appetite at its WORST?												
9. Your feeling drowsy (sleepy) at its WORST?												
10. Your having a dry mouth at its WORST?												
11. Your feeling sad at its WORST?												
12. Your vomiting at its WORST?												
13. Your numbness or tingling at its WORST?												

MM	Not Present										As Bad As You Can Imagine	
	0	1	2	3	4	5	6	7	8	9	10	
14. Your constipation at its WORST ?												
15. Your muscle weakness at its WORST ?												
16. Your diarrhea (loose stools) at its WORST ?												
17. Your sore mouth or throat at its WORST ?												
18. Your rash at its WORST ?												
19. Your problem with Paying Attention (Concentrating) at its WORST ?												
20. Your bone aches at its WORST ?												

Part II. How have your symptoms interfered with your life?

Symptoms frequently interfere with how we feel and function. How much have your symptoms interfered with the following items ***in the last 24 hours***:

	Did Not Interfere										Interfered Completely	
	0	1	2	3	4	5	6	7	8	9	10	
21. General activity?												
22. Mood?												
23. Work (including work around the house)?												
24. Relations with other people?												
25. Walking?												
26. Enjoyment of life?												

APPENDIX C: EORTC QLQ-C30 TOOL

ENGLISH

EORTC QLQ-C30 (version 3)

We are interested in some things about you and your health. Please answer all of the questions yourself by circling the number that best applies to you. There are no "right" or "wrong" answers. The information that you provide will remain strictly confidential.

Please fill in your initials:

--	--	--	--	--

Your birthdate (Day, Month, Year):

--	--	--	--	--	--	--

Today's date (Day, Month, Year):

31

--	--	--	--	--	--	--

	Not at All	A Little	Quite a Bit	Very Much
1. Do you have any trouble doing strenuous activities, like carrying a heavy shopping bag or a suitcase?	1	2	3	4
2. Do you have any trouble taking a long walk?	1	2	3	4
3. Do you have any trouble taking a short walk outside of the house?	1	2	3	4
4. Do you need to stay in bed or a chair during the day?	1	2	3	4
5. Do you need help with eating, dressing, washing yourself or using the toilet?	1	2	3	4

During the past week:

	Not at All	A Little	Quite a Bit	Very Much
6. Were you limited in doing either your work or other daily activities?	1	2	3	4
7. Were you limited in pursuing your hobbies or other leisure time activities?	1	2	3	4
8. Were you short of breath?	1	2	3	4
9. Have you had pain?	1	2	3	4
10. Did you need to rest?	1	2	3	4
11. Have you had trouble sleeping?	1	2	3	4
12. Have you felt weak?	1	2	3	4
13. Have you lacked appetite?	1	2	3	4
14. Have you felt nauseated?	1	2	3	4
15. Have you vomited?	1	2	3	4
16. Have you been constipated?	1	2	3	4

Please go on to the next page

During the past week:

	Not at All	A Little	Quite a Bit	Very Much
17. Have you had diarrhea?	1	2	3	4
18. Were you tired?	1	2	3	4
19. Did pain interfere with your daily activities?	1	2	3	4
20. Have you had difficulty in concentrating on things, like reading a newspaper or watching television?	1	2	3	4
21. Did you feel tense?	1	2	3	4
22. Did you worry?	1	2	3	4
23. Did you feel irritable?	1	2	3	4
24. Did you feel depressed?	1	2	3	4
25. Have you had difficulty remembering things?	1	2	3	4
26. Has your physical condition or medical treatment interfered with your family life?	1	2	3	4
27. Has your physical condition or medical treatment interfered with your social activities?	1	2	3	4
28. Has your physical condition or medical treatment caused you financial difficulties?	1	2	3	4

For the following questions please circle the number between 1 and 7 that best applies to you29. How would you rate your overall health during the past week?

1 2 3 4 5 6 7

Very poor

Excellent

30. How would you rate your overall quality of life during the past week?

1 2 3 4 5 6 7

Very poor

Excellent

